### 1.1. Summary of Changes

Reason for Change	Section
Added optional genetic blood sample collection	Table 2, Section 14.3.2
Clarified the BMI upper range as 40.0 at screening in Inclusion Criterion #4	Synopsis, Section 8.1
Clarified contraception requirements in Inclusion Criterion #8	Synopsis, Section 8.1, Section 11.2
Clarified obesity exclusion medication use in Exclusion Criterion #5	Synopsis, Section 8.2
Clarified when a participant may be enrolled who has uncontrolled thyroid disease in Exclusion Criterion #10	Synopsis, Section 8.2
Clarified prohibited medications in Exclusion Criterion #17	Synopsis, Section 8.2
Clarified Exclusion Criterion #18 regarding various diseases and reasons for exclusion	Synopsis, Section 8.2
Updated Exclusion Criterion #33 to be consistent with Section 14.2: Blood pressure should be taken seated not semi-recumbent and after resting 5 minutes	Synopsis, Section 8.2
Added clarification to Exclusion Criterion #36 regarding the use of benzodiazepines	Synopsis, Section 8.2
Added hemoglobin and hemoglobinopathy to Exclusion Criterion #41	Synopsis, Section 8.2
Added clarification to Exclusion Criterion #44 pertaining to interpretation of efficacy and/or safety results	Synopsis, Section 8.2
Added Exclusion Criterion #47 regarding use of opiate medications	Synopsis, Section 8.2
Added Exclusion Criterion #48 regarding use of medications that affect body weight	Synopsis, Section 8.2

Administrative	
Clarified which exclusion criteria need to be confirmed prior to randomization Fixed Day 57/Week 8 column heading error on 2 nd page of Table 2	Table 2
Added stimulant and opiate medications to the Prohibited Medications list	Section 10.1
Clarified diet and activity counseling will be limited to the protocol guidelines	Section 11.1
Clarified dosing interruptions procedures due to subject error	Section 13.4.3

## 2. SYNOPSIS

Name of Sponsor/Company: Kallyope, Inc.		
Name of Investigational Product: K-757, K-833		
Name of Active Ingredients: K-757 [REDACTED], K-833 [REDACTED]		
Protocol Number: P006-03	Phase: 2	Country: USA
Title of Study: A Randomized, Placebo-Controlled, Double-Blind 13-Week Study to Evaluate the Safety, Tolerability, and Weight Loss Efficacy of K-757 alone and in Combination with K-833 in Participants who are Obese		
Study center(s): Multi-center study in US		
Studied period (years): 12 months Estimated date first patient enrolled: Oct 2023 Estimated date last patient completed: Jul 2024		Phase of development: 2
Number of participants (planned): Approximately 150 (50 per treatment group)		
Objectives: In participants who are obese: Primary: To assess relative (%) change from baseline in body weight after 13 weeks of treatment with K-757 alone and in combination with K-833, in comparison to placebo. Hypothesis: At least one of the treatment arms is superior to the placebo arm in reducing body weight calculated as percentage change from baseline after 13 weeks of treatment. Secondary: 
 
To assess the proportion of participants achieving <math>\geq 5\%</math> weight loss from baseline after 13 weeks of treatment with K-757 alone and in combination with K-833, in comparison to placebo.
 
To assess the absolute change from baseline in body weight after 13 weeks of treatment with K-757 alone and in combination with K-833, in comparison to placebo.
 
To characterize the safety and tolerability of K-757 alone and in combination with K-833 over 13 weeks of treatment.
 
 Exploratory: 
 
To assess the change from baseline in hemodynamic parameters (systolic blood pressure, diastolic blood pressure and heart rate) after 13 weeks of treatment with K-757 alone and in combination with K-833, in comparison to placebo.
 
To assess the change from baseline in total cholesterol, low-density lipoprotein (LDL), high-density lipoprotein (HDL), and triglycerides after 13 weeks of treatment with K-757 alone and in combination with K-833, in comparison to placebo.
 
 Study Design: This is a randomized, double-blind, placebo-controlled 13-week study to evaluate the efficacy of K-757 alone and in combination with K-833 versus placebo in participants who are obese without type 2 diabetes mellitus (T2DM). Approximately one hundred fifty (150) participants will be enrolled and randomized (1:1:1) to receive K-757 alone, K-757+K-833, or matching placebos.		

**Study Schematic**

- a Screening will occur over up to 4 weeks prior to randomization.
- b Refer the Dosing Table and Section 5.4.1 for study drug administration details
- c Week indicates the duration of treatment completed prior to the visit, not the week in which the visit occurs. For example, the “Week 1” visit is targeted to occur on Day 8 (the first day of the 2nd week of treatment).

The study will be comprised of a Screening period (up to 28 days prior to randomization), a 13-week double-blind Treatment period (dosing on Days 1 to 91; end-of-treatment visit Day 92), and a post-study Follow-Up period (approximately 14 days after their last dose). There will be 13 weeks of dosing (Days 1 through 91). The total duration of the study for each participant will be up to approximately 19 weeks. Randomization will be stratified by gender (male/female). Enrollment into each gender strata will be capped at 70% (ie. neither gender may exceed 70% of total enrollment).

**Dosing Table**

Arm	Time (AM/PM)		Week			
			Week 0 (D1-7)	Week 1 (D8-14)	Week 2 (D15-21)	Week 3 through 13 (D22-92)
K-757+K-833	AM	757/833 (mg)	30/100	30/100	60/100	120/100
	PM	757/833 (mg)	pbo/pbo	30/100	60/100	120/100
K-757 alone	AM	757/833 (mg)	30/pbo	30/pbo	60/pbo	120/pbo
	PM	757/833 (mg)	pbo/pbo	30/pbo	60/pbo	120/pbo
Placebo to K-757 and K-833	AM	757/833 (mg)	pbo/pbo	pbo/pbo	pbo/pbo	pbo/pbo
	PM	757/833 (mg)	pbo/pbo	pbo/pbo	pbo/pbo	pbo/pbo

Refer to Section 5.4.1 for additional titration information.

Participants will return to the trial site at the times described in the study schematic and schedule of assessments (SOA) to complete study procedures. During two of the on-treatment weeks when participants do not return to the trial site, the site will contact the participants by phone in order to assess study medication compliance, new concomitant medication use, and adverse events (AEs).

Starting at the randomization visit (Visit 2), all participants will receive nutritional and physical activity counseling from a dietician, or a similarly qualified healthcare professional designated by primary investigator. Nutritional counseling will focus on calorie-reduction (-500 kcal/day). This counseling will occur at randomization (Visit 2), twice during the treatment phase (Visit 6 and Visit 9), and at the post-Study follow-up visit.

Safety and tolerability will be assessed in an ongoing fashion through physical examination, vital sign assessment, 12-lead electrocardiogram (ECG), clinical laboratory assessments, and collection of serious and non-serious AEs. Specific time points are described in the SOA Table 2.

Plasma will be obtained for pharmacokinetics (PK) and potential pharmacodynamics (PD) at select time points during treatment (Table 2).

To mitigate mechanism-related GI intolerance, K-757 will be titrated according to the Dosing Table (see above). In the combination arm and the K-757-only arm K-757 will be titrated to the maintenance dose of 120 mg twice daily (BID) by Day 22. K-833 will be initiated at 100 mg QAM and will be titrated to the maintenance dose of 100 mg BID on Day 8.

For participants experiencing gastrointestinal (GI) intolerance, all reasonable, medically appropriate efforts should be made to support them in adhering to scheduled dosing (see Section 7.1.1).

### **Subject/Criteria for Entry into the Trial**

#### **Inclusion criteria:**

All entry criteria, including laboratory test results, need to be confirmed before administration of the first dose of study drug.

In order to be eligible for participation in this trial, the subject must:

1. Understand the trial procedures and agree to participate by providing written informed consent prior to trial related activities. Trial-related activities are any procedures that are carried out as part of the trial, including activities to determine suitability for the trial.
2. Be willing and able to comply with the study schedule of visits, all trial procedures and restrictions, including following study diet requirements.
3. Be a male or female, age 18 to 70 years, inclusive, at the time of signing informed consent.
4. Have a body mass index (BMI) of 30.0 to 40.0. kg/m^2, inclusive at screening.
5. History of at least one self-reported unsuccessful dietary effort to lose body weight.
6. Be weight stable (<5% variation) over the last 3 months (by subject report).
7. Be a nonsmoker or has smoked ≤10 cigarettes per week for at least 3 months and agrees not to exceed this for the duration of study participation; has not used other nicotine containing products (e.g. other forms of tobacco, nicotine patch, e-cigarettes, vapes) for at least 3 months and agrees to abstain from such products throughout study participation.
8. Meet the following requirements:
  - a. Is a male who agrees to **all** of the following:
    - If partner is a non-pregnant female of child-bearing potential: To use an appropriate method of contraception, which must include a condom with spermicidal cream or jelly, from the first dose of study drug until 14 days after the last dose of study drug. A male subject who has had a vasectomy procedure must use a condom but is not required to use spermicidal cream or jelly.
    - If partner is pregnant, to use a condom

OR

b. Is a female who is of non-childbearing potential defined by at least 1 of the following criteria:

- Postmenopausal (aged >45 years and with a minimum of 12 months of spontaneous amenorrhea with a Screening serum follicle-stimulating hormone (FSH) level in the menopausal range established for the central laboratory.
- Post hysterectomy, bilateral oophorectomy or bilateral salpingectomy, based on the subject's recall of their medical history.

OR

c. Is a female of reproductive potential and:

- agrees to not donate eggs from the first dose of study drug until 14 days after the last dose of study drug.
- agrees to remain abstinent from heterosexual activitya or
- agrees to use (or have their partner use) a birth control method that is highly effective and has low user dependency from the first dose of study drug until 14 days after the last dose of study drug. Acceptable methods of birth control are:
  - Progestogen-only implant (e.g. etonogestrel implant)
  - Intrauterine device (IUD)
  - Intrauterine hormone-releasing system (IUS)
  - Bilateral tubal occlusion
  - Vasectomized partner

a Abstinence can be used as the sole method of contraception if it is in line with the subject's preferred and usual lifestyle and if considered acceptable by local regulatory agencies and ethics committees. Periodic abstinence (e.g., calendar, ovulation, sympto-thermal, post-ovulation methods, etc.) and withdrawal are not acceptable methods of contraception. This condition is waived if the subject is proven to have no child-bearing potential (eg, hysterectomy).

**Exclusion criteria:**

Participants are excluded from the trial if any of the following criteria apply:

Glycemia related:

1. Has a hemoglobin A1c (HbA1c)  $\geq 6.5\%$  (48 mmol/mol) as measured by the central laboratory at screening.
2. Has a history of clinically significant endocrine disease including T2DM.  
**Note:** A history of hypothyroidism does not require exclusion if the subject has been on a stable dose of thyroid hormone replacement (thyroxine) for at least 3 months prior to screening and the screening thyroid-stimulating hormone (TSH) is within the central laboratory normal range.
3. Has a history of type 1 or type 2 diabetes mellitus.
4. Had treatment with any glucose-lowering agent(s) within 90 days before screening.

Obesity related:

5. Had treatment with any medication approved for the treatment of obesity or any investigational agent being tested for obesity treatment within the past 6 months before screening. This includes agents that are approved as a component of a multi-drug combination treatment for obesity, regardless of the purpose of current use, with the exception of bupropion.

Bupropion, which is a component of the naltrexone-bupropion combination approved for weight loss (ContraveTM), is also approved as a single agent for the treatment of depression. Bupropion is not

exclusionary if it is being used for treatment of depression and eligibility criteria for anti-depressant medication stability prior to screening are met (see Exclusion Criterion #12).

6. Has been treated with/used any other medication, supplement, or device for the purpose of promoting weight loss (regardless of whether they are approved or promoted for the purpose of weight loss) in the 90 days prior to screening.
7. Treatment with any glucagon-like peptide-1 (GLP-1) receptor agonist in the prior 6 months.
8. Participation in an organized weight reduction program (e.g. Weight Watchers) within 90 days of screening.
9. Had a previous or has a planned (during the trial period) obesity treatment with surgery or a weight loss device. **Note:** Prior liposuction and/or abdominoplasty are not exclusionary if performed >2 years before screening).
10. Has uncontrolled thyroid disease, defined as thyroid stimulating hormone (TSH) outside (above or below) the reference range of the central laboratory at screening or has any history of Grave's disease unless all 3 of the following criteria are all met: 1. Grave's disease was treated with total thyroidectomy >2 years prior to screening, 2. There has been no recurrence of hyperthyroidism since thyroidectomy, **and** 3. TSH is the reference range of the central laboratory at screening.
11. Obesity is induced by an endocrine disorder (e.g. Cushing's disease).

Mental health:

12. Has a history of major depressive disorder within 2 years before screening unless **all** of the following criteria are met:
  - a) the depressive disorder has always been unipolar (no history of mania or hypomania)
  - b) in the opinion of the investigator, depressive symptoms have been stable and well controlled for  $\geq 2$  years prior to screening.
  - c) any anti-depressant drug-treatment regimens (medications and doses) have been stable for  $\geq 6$  months prior to screening.
13. Has any history of other severe psychiatric disorder (e.g., schizophrenia, bipolar disorder) that was not clearly attributable to an intercurrent event/life circumstance, self-limited and fully resolved  $\geq 1$  year prior to screening.
14. On the screening Patient Health Questionnaire-9 (PHQ-9), has an overall score  $\geq 15$  **or** has a score  $> 0$  for Question # 9 (Thoughts that you would be better off dead or of hurting yourself)([Appendix C](#)).  
**Note:** See Section 15.1.6 regarding requirements for referral to a mental health professional based on the results of the screening PHQ-9 assessment.
15. Has any lifetime history of suicide attempt or suicidal behavior. **Note:** Suicidal behavior includes any acts/preparation toward making a suicide attempt whether the attempt is never initiated or is initiated but interrupted by self or another person .
16. Use of any anti-psychotic agents for any purpose within 2 years before screening.
17. Use of the following prohibited agents:
  - Prohibited classes of anti-depressant agents (see Section 10.1), for any purpose, within 6 months of screening. **Note:** Use of allowable classes of anti-depressant agents (see Section 10.1) is permitted **only** if the anti-depressant regimen (agents **and** doses) has been stable for  $\geq 6$  months prior to screening and is not anticipated to change during the trial period.
  - Stimulant medications including amphetamines (e.g. dextroamphetamine, lisdexamfetamine) and methylphenidate/dexmethylphenidate within 6 months of screening.

General Safety:

18. Has a recent history (within the past 3 years of the screening visit) or current diagnosis or evidence of hematological, immunological, renal, respiratory, neurologic, or genitourinary abnormalities or

diseases that, per the investigator's judgement, may jeopardize the subject's safety or compliance with the protocol, or otherwise interfere with interpretation of efficacy and/or safety results.

19. Has a recent history (within past 3 years of the screening visit) or current diagnosis of any of the following GI (gastro-intestinal) related diseases: intestinal obstruction, GI perforation, adhesions, *Clostridium difficile* colitis or have had recent unexplained GI bleeding within 3 months prior to screening.
20. Has any history of pancreatitis (acute or chronic), gastroparesis, ischemic colitis, inflammatory bowel disease (IBD), or celiac disease.
21. Has any personal or first-degree relative history of multiple endocrine neoplasia type 2 or medullary thyroid carcinoma.
22. Has a screening estimated Glomerular Filtration Rate (eGFR) estimated with the Modification of Diet in Renal Disease (MDRD) equation of  $<60$  ml/min/1.73 m^2.
23. Has a history of malignant neoplasms within the past 5 years prior to screening. Basal and squamous cell skin cancer and any carcinoma in-situ are allowed if they have received treatment and follow-up consistent with local standard of care.
24. Has any history of cardiovascular disease including stable and unstable angina pectoris, myocardial infarction, transient ischemic attack, stroke, cardiac decompensation, clinically significant arrhythmias, clinically significant conduction disorders, or any history of heart failure.
25. Has any surgery scheduled for the duration of the trial, except for minor surgical procedures, in the opinion of the investigator.
26. Has a history of human immunodeficiency virus (HIV) infection.
27. Has any active liver disease other than non-alcoholic fatty liver disease (NAFLD), or any gallbladder disease that has been active/symptomatic within 6 months of screening.
28. Has a positive test result for hepatitis B surface antigen (Ag), hepatitis C virus antibody, or HIV antibody, at the Screening Visit. Note: Participants with positive hepatitis B virus or hepatitis C virus serology may be enrolled if quantitative polymerase chain reaction for hepatitis B virus or hepatitis C virus ribonucleic acid is negative.
29. Has alanine aminotransferase or aspartate aminotransferase (ALT or AST) of  $>2.0X$  upper limit of normal (ULN) or total bilirubin  $>1.5X$  ULN at the Screening visit. Note: An isolated bilirubin  $>1.5X$  ULN is acceptable if bilirubin is fractionated, and direct bilirubin is within the laboratory normal range.
30. Has serum amylase or lipase  $>1.2X$  the ULN at the Screening visit.
31. Has a triglycerides value of  $>600$ mg/dL at the Screening visit (if value is  $\geq 600$  mg/dL and the sample was obtained in the non-fasted state, a repeat fasting determination may be obtained to assess eligibility).
32. Has a corrected QT interval to Fridericia's formula (QTcF)  $>450$  milliseconds (msec) for males and  $>470$  msec for females at screening.
33. Has a mean value for triplicate seated systolic blood pressure  $>160$  mmHg and/or diastolic blood pressure (BP)  $>95$  mmHg measured after at least 5 minutes at rest at the Screening Visit.  
**Note:** If a subject's BP is exclusionary on the first triplicate assessment at the Screening visit, they may have 1 repeat triplicate BP assessment at that visit after another rest of at least 10 minutes.  
If a participant's BP is exclusionary on 2 assessments at the Screening visit, the investigator can, at their discretion, adjust and/or add anti-hypertensive medications and re-assess triplicate BP up to twice prior to dosing at the Randomization visit (Visit 2). Anti-hypertensive regimens must align with the requirements detailed in Section 10.1 ( $\leq 2$  agents that do **not** include verapamil)  
If a participant's BP is exclusionary at the Screening visit and the Randomization visit (Visit 2), they must be excluded.

34. Has known history or suspected abuse of alcohol or recreational drugs at Screening.
35. Has excessive consumption of alcohol within 6 months prior to screening (>14 drinks/week for men and >7 drinks/week for women, where 1 drink= 5 ounces [150 mL] of wine or 12 ounces [360 mL] of beer or 1.5 ounces [45 mL] of hard liquor) or use of soft drugs (such as marijuana or any substances containing tetrahydrocannabinol (THC) or cannabidiol (CBD)) within 3 months prior to Screening, or hard drugs (such as cocaine) within 6 months prior to Screening.
36. Has a positive drug screen at Screening. Note: If benzodiazepines are detected on the drug screen, this is not exclusionary if they are prescribed a benzodiazepine for a therapeutic purpose (e.g. for insomnia) and confirmatory documentation is obtained from the prescribing physician.
37. Has known or suspected hypersensitivity to trial product(s) or related products.
38. Has a history of multiple significant and/or any severe allergies (e.g., food, drug, latex allergy) or has had an anaphylactic reaction or significant intolerance to prescription or nonprescription drugs or food.
39. Has previous participation in this trial. Participation is defined as signed informed consent.
40. Has participated in any clinical trial of an approved or non-approved investigational medicinal product within 90 days before screening.
41. Had major surgery or donated or lost 1 unit of blood (approximately 500 mL) within 4 weeks prior to the Screening Visit; has a screening hemoglobin <11.0 g/dL (males) or <10.0 g/dL (females), or has a known hemoglobinopathy (e.g. sickle cell anemia, hemolytic anemia).
42. Is a female who is pregnant, breast-feeding or intends to become pregnant during the planned course of the study. **Note:** Participants must have a negative serum pregnancy test ( $\beta$ -human chorionic gonadotropin ( $\beta$ -hCG)) performed by the central laboratory prior to enrollment in the study and prior to the randomization visit.
43. Is currently in violation of study requirements for prohibited and permissible concomitant medications or is anticipated to violate these requirements during study participation. These requirements are detailed in Section 10.1.
44. Has any disorder, unwillingness or inability, not covered by any of the other exclusion criteria, which in the investigator's opinion, might jeopardize the subject's safety or compliance with the protocol, or otherwise interfere with interpretation of efficacy and/or safety results.
45. Is unable or unwilling to follow the study nutritional and physical activity counseling and to refrain from alternative lifestyle modification strategies throughout study participation. Refer to Section 10.
46. Is an employee or immediate family member (e.g., spouse, parent, child, sibling) of the Sponsor or study site.
47. Has any use of opiate medications within 14 days of screening or any anticipated/potential use of opiates during study participation.
48. Use of any other medications within 6 months of screening that, in the investigator's judgement, can significantly impact (increase or decrease) body weight, regardless of the purpose for their use.

**Note:** Rescreening/retesting is not permitted unless specified above.

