#### 4.5 Per Protocol Analysis Set

The per protocol analysis set consist of all participants who completed 13-week treatment and have weight assessment at week 13 and treatment compliance >=80%. Participants who completed treatment but have week 13 assessment done more than 3 days after last dose date and participants whose weights at week 13 are collect at non-fasted state are excluded.

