#### 5.2 Subject Disposition

The number and percentage of participants who were randomized, who were randomized but did not receive the study drug as randomized, who were treated with the study drug, who completed the double-blind treatment and/or the study, who prematurely discontinued the study drug and/or study and the primary reason discontinuation (study drug and/or study) will be summarized by treatment group and overall.

A separate summary will be provided for the number and/or percentage of subjects that were screened, enrolled and screened failed (including initial screen and re-screen) and reason for screen failure.

Subject disposition will be listed for all randomized participants. Also, the eligibility status for the study will be listed for all screened participants, using the Screened Set.

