#### 5.3 Protocol Deviations

Protocol deviations identified during the course of the study will be classified as major or minor.

A major protocol deviation (sometimes referred to as a protocol violation or a significant protocol deviation) is a deviation to the protocol that might significantly impact the completeness, accuracy or reliability of the study data or that may significantly affect a participant's rights, safety or well-being.

Before the database lock, all protocol deviations will be reviewed by the Sponsor. Final determination of major deviations is the responsibility of the Sponsor. Major protocol deviations will be identified and listed in the CSR.

Major protocol deviations will be summarized by treatment group and overall, and by category and sub-category if there is a sufficient number of major protocol deviations.

All protocol deviations will be presented in a listing. A by-subject listing will be provided for major protocol deviations.

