#### 5.8.1.4 Completer Analysis

Completer analysis will also be performed. The only attributes that changes from the definition of the primary estimand is that analysis is done for per protocol analysis set, ie only participants who complete 13-week treatment and with a week 13 assessment and treatment compliance >=80% will be included for analysis. Participants who completed treatment but have week 13 assessment done more than 3 days after last dose date and participants whose weights at week 13 are collect at nonfasted state will be excluded from analysis.

Additional sensitivity analysis may be performed using multiple imputation (MI) approach.

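### The per-protocol set takes no account of major deviations likely to affect body weight, so the supportive completer analysis can retain weight-related entry breaches, prohibited weight-affecting drugs and wrong-drug receipt

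*Protocol*

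**What the plan says.** SAP 4.5 gives a complete membership rule: "The per protocol analysis set consist of all participants who completed 13-week treatment and have weight assessment at week 13 and treatment compliance >=80" per cent. It then removes two groups. The first is completers whose Week 13 assessment came over 3 days after the final dose. The second concerns fasting: "participants whose weights at week 13 are collect at non-fasted state are excluded". SAP 5.8.1.4 repeats the rule for the completer analysis and states: "The only attributes that changes from the definition of the primary estimand is that analysis is done for per protocol analysis set".

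SAP 5.3 has the sponsor review all deviations before database lock and decide which are major. A major deviation "is a deviation to the protocol that might significantly impact the completeness, accuracy or reliability of the study data". The definition also takes in deviations that bear on rights, safety or well-being. The stated uses are listings and, if there are enough of them, summaries. No analysis set refers to them.

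Several protocol rules bear directly on the weight endpoint:

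- Inclusion 6 requires stable weight over the previous 3 months.
- Exclusions 5 to 9 and 48 cover recent obesity drugs, other weight-loss products, weight programmes, surgery or devices, and other weight-altering drugs. Exclusion 7, for instance, is "Treatment with any glucagon-like peptide-1 (GLP-1) receptor agonist in the prior 6 months".
- Section 10.1 prohibits weight-loss medication (item 4) and any other drug judged able to change weight significantly (item 12) during the study.

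SAP 5.2 provides a disposition count of participants "who were randomized but did not receive the study drug as randomized".

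**The concern.** A set called per protocol would ordinarily leave out people whose outcome was materially affected by a breach of the protocol. This one removes a participant whose Week 13 weight was not fasted. It keeps a compliant completer who entered soon after a GLP-1 receptor agonist, took a prohibited weight-loss drug on study, or was given another arm's capsules. For such a person, part of the weight change may reflect regain after an earlier drug, a drug outside the trial, or the wrong trial arm.

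No other specified efficacy analysis fills the gap. The primary and treatment-policy analyses use the mITT set and properly keep deviators. The optional multiple-imputation analysis in SAP 5.8.1.4 deals with missing data. The plan therefore contains no efficacy analysis showing whether the result holds without weight-relevant deviators. If one were added after unblinding, the choice of exclusions would be post hoc.

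**Working it through.** **Reading the rules side by side**

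| Event in a participant who completes 13 weeks | Removed by SAP 4.5 / 5.8.1.4? |
|---|---|
| Compliance below 80% | Yes |
| Week 13 weight more than 3 days after last dose | Yes |
| Week 13 weight not fasted | Yes |
| Breach of Inclusion 6 or Exclusions 5–9 or 48 | No |
| On-study use of a drug prohibited by Protocol 10.1 item 4 or 12 | No |
| Received study drug other than that randomised | No |

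On the last row, compliance in SAP 5.7.2 counts days with full AM and PM doses, whichever drug was in the capsules. Only the analysis set changes from the primary estimand, and the mITT set is analysed as randomised, so the participant counts under the randomised arm.

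**Does discontinuation remove these people anyway?** Only in part. Protocol 8.3.1.1 lists a significant protocol deviation among the recorded reasons for stopping treatment, but not among its five mandatory discontinuation criteria. Under Protocol 10.1, a need for prohibited medication may lead to stopping study drug, and a participant can continue with sponsor agreement. A breach found only after Week 13 cannot lead to stopping at all.

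**The plan's own figure**

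Inputs from SAP 3.4: 50 per arm, 20% dropout, SD 4%, difference 4 points, two-sided alpha 0.05. Evaluable per arm: 50 × 0.80 = 40.

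- SE = 4 × √(2/40) = 0.894
- 4 / 0.894 = 4.472, and 4.472 − 1.960 = 2.512
- Power = Φ(2.512) = 0.994, consistent with the stated figure of more than 95%.

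**Illustrative effect of retained deviators**

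The documents give no deviation rate, so these inputs are assumptions. The per-protocol set has 50 × 0.80 × 0.90 = 36 per arm, where the 90% meeting the other conditions is assumed. A number k of deviators all fall in one arm, each with a weight change d points away from what it would otherwise have been.

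- SE of the difference = 4 × √(2/36) = 0.943
- Shift in the difference = k × d / 36

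| k | d = 5 | d = 8 | d = 10 |
|---|---|---|---|
| 1 | 0.14 | 0.22 | 0.28 |
| 2 | 0.28 | 0.44 | 0.56 |
| 3 | 0.42 | 0.67 | 0.83 |

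The range is 0.14 to 0.83 points, or 0.14/0.943 = 0.15 to 0.83/0.943 = 0.88 standard errors. If one deviator with d = 8 falls in each of the two arms compared, the shift is 8/36 − 8/36 = 0. For wrong-drug receipt, a natural size for d is the design difference itself: two participants at 4 points give 2 × 4/36 = 0.22 points, or 0.24 SE.

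**Cost of excluding deviators**

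The same power formula, starting from 40 per arm, with the removed shares assumed:

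| Further removed | Per arm | Power |
|---|---|---|
| 5% | 38 | 0.992 |
| 10% | 36 | 0.989 |
| 20% | 32 | 0.979 |
| 30% | 28 | 0.963 |

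**The case against.** The strongest reply is that SAP 5.8.1.4 is headed as a completer analysis and does what that name says. No decision rule depends on it, and the primary analysis is on the mITT set. Entry criteria must be confirmed before the first dose, and prohibited medication is rechecked just before randomisation. The group at issue is therefore only undetected or tolerated breaches among compliant completers. Entry breaches precede blinded randomisation, so they are independent of arm and their expected net bias is zero. The same deviators are also in the mITT set, so keeping them in both analyses is not a natural source of disagreement.

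Most of this stands, and it limits the importance of the point. It does not remove the gap: the rule in SAP 4.5 is complete as written and admits these participants. The argument about randomisation also does not cover on-study drug use, which happens after randomisation and could differ by arm.

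Two stronger readings are tempting. A reader might infer that the set ignores every major deviation. It does not: it acts on low compliance and on late or non-fasted Week 13 weights, and a participant stopped for a deviation is no longer a completer. A reader might also infer that SAP 5.3 declares these participants' weights unreliable. Its wording is conditional, is not specific to weight, and extends to rights and safety deviations that need not touch weight.

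**Conclusion.** The gap is real and minor. The per-protocol set is defined by completion, compliance and the conditions of the Week 13 weight. The deviation review already planned in SAP 5.3 does not feed it. Compliant completers with a weight-related entry breach, on-study use of a prohibited weight-affecting drug, or receipt of study drug other than that randomised stay in the supportive analysis under the randomised arm.

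The size cannot be known from the documents. The 0.14 to 0.83 points rests on 36 per arm, SD 4%, and one to three deviators all in one arm and all shifted the same way by 5 to 10 points. That is an unfavourable arrangement. Entry breaches spread across arms would mostly add noise. A reader might infer that the trial's main result is at risk. The documents do not support that, because the primary analysis is on the mITT set and does not depend on this one.

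**What to change.** Add to SAP 4.5, and mirror in 5.8.1.4, wording to this effect:

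> Participants are also excluded if they have (a) a major protocol deviation likely to affect body weight, namely a breach of Inclusion 6 or of Exclusions 5 to 9 or 48, or on-study use of prohibited weight-affecting medication (Protocol 10.1 items 4 and 12), as determined by the sponsor while blinded before database lock; or (b) received study drug other than that randomised, identified after unblinding from the record of actual versus randomised treatment. Exclusions are listed by reason and arm.

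Part (b) has to be a fixed, pre-specified rule rather than a blinded judgement. Under SAP 3.3 and 3.3.1.4 the sponsor and biometrics staff are blinded until lock, and confirming that another arm's drug was taken needs allocation data.

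The cost is a short SAP change using information already collected, and a slightly smaller supportive set. Power for the design difference stays at 0.963 even if a further 30% are removed from 40 per arm. Excluding on on-study drug use selects on a post-randomisation event, but the set already does so through completion and compliance. The listing by reason and arm lets a reader see whether exclusions were uneven.
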